1.2	[name]	[name]	27-Oct-2019	 FDA Review: Added sentence for clarification (Chapter 6): Participants will download the study equipment approximately one time per week or as frequently as needed. Added sentence for clarification (section 9.5): Participants will be instructed to download the study devices (i.e. insulin pumps, CGM, ketone meters, activity tracker, etc) each week, or as needed, to secure data collection, except the ketone meter which will assess ketosis events). Added to Ketoacidosis Management (section 10.5): Experimental participants will be advised to check ketones if symptoms consistent with ketoacidosis occur even if blood glucose is not elevated. Added to Adverse Event (section 13.1.1): now includes study drug in definition. Modified sentence (section 13.2.2): Ketosis as defined by symptoms and ketones regardless of treatment provided in a health care facility. Modified participants' stopping rules (section 13.9.1):

				 Two distinct episodes of DKA that are not attributable to the study drug One distinct episode of DKA directly attributable to the study drug
1.3	[name]	[name]	30-Oct-2019	 FDA Review: Inserted that study drug is not approved for use in T1DM patients (section 1.2). Inserted User Manual language regarding the pumps response to missing CGM data (section 9.6).
1.4	[name]	[name]	01-Nov-2019	 IRB Pre Review Comments from 04-Oct-2019. Added that Equipment training in the Pilot Study is intended to begin immediately after screening eligibility has been met (section Chapter 6). Clarified sentence to read that staff & participants will be at the hotel admission (section 7.1).
1.5	[name]	[name]	24-Mar-2020	 Study Team Modifications: DSMB reduced Empagliflozin from 10 mg/daily to 5 mg/daily post-pilot study review. Empagliflozin dosage instructions (section 3.3). The study physician will determined screening test(s) needed for pilot participants to proceed to the Main Study. (section 4.1). Corrections to the Glycemic Treatment Guidelines (section 7.5). Virtual study visits may take the place of in-person study visits (Chapter 9). Participants will be asked to record two days of baseline ketone values before initiating the use of the study drug (section 9.1.1). Ketone meters will no longer be downloaded each week (section 9.5).

				 Study participants will log daily ketone values in an online resource for ongoing assessment purposes (section 9.5). Blood glucose check in section 10.3 conflicts with section 7.4. Clarified that Pregnancy will not be considered an adverse event (section 13.1.1). A Data and Safety Monitoring Board (DSMB) will review compiled safety data after the completion of 10 Main Study participants. As a safety measure, the Board will review if the rate of mild ketosis greater than 40% (B-OH-B level > 0.6 mmol), 20% significant ketosis (B-OH-B > 1.5 mmol) and more than 5% DKA (B-OH-B > 3 mmol) to be considered significant to stop the study (section 8.3). Other miscellaneous corrections throughout document.
1.6	[name]	[name]; [name]	06-Apr-2020	 Response to FDA questions 03-Apr-2020: Clarified the Pilot participants lab work needed to proceed into Main Study: Pilot participants may enroll the Main Study. The study physician may request repeat laboratory values if values are greater than 6 weeks from Pilot screening laboratory values. A current urine/blood pregnancy test will be required prior to enrolling into the Main Study (section 4.1). Added for clarification: Main Study participants who did not participate in the Pilot Study may use historical lab results that are dated within 2 weeks of the screening appointment (section 4.6). The study physician has the discretion to exclude a study participant if concerned about

			their safety in this trial (section 4.6).
1.7	[name]	10-Apr-2020	 Response to FDA questions 07-Apr-2020: Added: Empagliflozin is available only in 10 mg and 25 mg film coated unscored tablets. For this study, the participants will be provided 10 mg tablets and a pill splitter. They will be instructed to split only 1 tablet at a time and take each half tablet (5mg each) on subsequent days. Participants will be cautioned against spitting more than one tablet at a time (section 3.3). A Data and Safety Monitoring Board (DSMB) will review compiled safety data after 10 participants complete 4 weeks of the Main Study. Absence of serious adverse events related to Empaglifozin, the participants will continue with study participation pending DSMB review (section 8.3). Added: The study team will download the ketone meter whenever the study subject attends an in-clinic visit (section 9.5).

Endpoint	To demonstrate the efficacy of Empagliflozin as adjuvant therapy with Basal-IQ therapy vs a closed loop artificial pancreas system (CiQ-EMPA) in patients with T1DM. The primary efficacy outcome variable will be time in range (70-180 mg/dl).
Population	 Key Inclusion Criteria Age 18-65 Diagnosis of Type 1 Diabetes Key Exclusion Criteria Hemoglobin A1c > 9%
Sample Size	 Enrollment for the Pilot Study will proceed with the goal of completing approximately 5 participants in the trial. Enrollment for the Main Study will proceed with the goal of completing approximately 40 subjects, 10 subjects in each group.
Treatment Groups	 With Empagliflozin 5 mg daily: CiQ x 4 weeks (CiQ-EMPA) then Basal-IQ x 2 weeks (BiQ-EMPA) Basal-IQ x 2 weeks (BiQ-EMPA) then CiQ x 4 weeks (CiQ-EMPA) Without Empagliflozin: CiQ x 4 weeks (CiQ-NO EMPA) then Basal-IQ x 2 weeks (BiQ-NO EMPA) Basal-IQ x 2 weeks (BiQ-NO EMPA) then CiQ x 4 weeks (CiQ-NO EMPA)
Participant Duration	Approximately 10 weeks
Protocol Overview/Synopsis	Up to five participants will participate in a Pilot Study. These participants will wear the Basal-IQ insulin pump, continuous glucose monitor, and take one tab daily of Empagliflozin 10 mg for about 2-3 weeks at home. They will then participate in a 36-48 hour hotel admission to begin the use of Control-IQ System with Empagliflozin. After DSMB review of safety data, up to 40 participants will be enrolled to begin the Main Study where, in a crossover design, participants will use the Control-IQ for 4 weeks and then Basal-IQ for 2 weeks, with the drug given at the dosage of 5mg per day or without drug.

STUDY VISITS AND PROCEDURES SCHEDULE

	Screening	Hotel Admission	Randomization & Equipment Training	Control-IQ Use	Equipment Training	Basal-IQ Use	Equipment Training	Follow-Up
Location	Clinic/Virtual	about 36- 48 hours	Clinic/Virtual	Home x 4 weeks	Clinic/Virtual	Home x 2 weeks	Clinic/Virtual	Home
Informed Consent	x							
Eligibility Assessment	x							
Medical History	x							
HbA1c	x							
Blood Testing: TSH, CMP (additional labs as necessary)	x							
Pregnancy test (if applicable)	x	х	х	х	х	х	x	х
Electrocardiogram (ECG)	x							
Physical Exam	x							
Vital Signs (including height/weight)	x							
Randomization			х					
Questionnaires			х	Post Use		Post Use		х
Review diabetes management and AEs	x	х		х		х		х

1	Table of Contents
2	Chapter 1: Background 17
3	1.1 Introduction
4	1.2 Empagliflozin (SGLT-2 inhibitor) in TID17

96 97 98 99 100 101 102 103 104 105	Chapter 15 Statistical Consideration6215.1 Design and Randomization6215.2 Sample Size6415.3 Outcome Measures6515.4 Safety Analyses6615.5 Baseline Descriptive Statistics6615.6 Device Issues66Chapter 16 Data Collection and Monitoring6816.1 Case Report Forms and Device Data6816.2 Study Records Retention68

109	17.2 Institutional Review Boards	
110	17.3 Informed Consent Process	
111	Chapter 18 References	
112		
113		

114 Chapter 1: Background

115 **1.1 Introduction**

116 Current automated insulin delivery device systems providing dynamic insulin infusion, while 117 improving prandial glucose control compared to conventional open loop therapies, have been unable to normalize prandial glucose control in T1DM. Strategies that have been 118 119 used/considered in AP systems to improve prandial control include a) hybrid system that requires 120 the patient to announce meals by entering the carbohydrate content; b) system with meal 121 announcement that is partially or completely independent of meal carbohydrate content, and c) 122 fully automated system with no meal announcement. Notably, a fully automated CLC system would lower the significant patient burden linked to prandial glucose control. Postprandial 123 124 glucose control is a key determinant of HbA1c, the clinical gold standard for optimal glucose 125 control. While meal carbohydrate content is the major factor for prandial glucose excursions, precise determination of meal carbohydrate content (that is associated with better glycemic 126 127 control and lower glucose variability) during free living remains a significant challenge for the patients with an average error in carbohydrate counting of ~20% with most patients 128 129 underestimating their carbohydrate content hence leading to increased prevalence of prandial 130 hyperglycemia.

131 Clinical trials with fully automated AP systems have mostly been in small number of patients and 132 in the in-patient settings for short durations [1, 2]. These trials have demonstrated significant 133 postprandial hyperglycemia with a risk for late postprandial hypoglycemia. The availability of 134 newer antidiabetic drugs provide the opportunity to test these medications as adjuvants together with conventional or CLC algorithms, to determine the effects, if any, of combination 135 136 therapy, for improvements in postprandial and overall glucose control in individuals with T1DM. 137 The adjuvants that have been tried in very short-term inpatient trials include pramlintide (amylin 138 analogue that delays gastric emptying and lowers postprandial glucagon concentrations) [3-5] 139 and Glucagon-like-peptide 1 receptor analogues (delays gastric emptying and lowers 140 postprandial glucagon concentrations) and GLP-1 receptor agonists [6]. These studies have 141 demonstrated modest improvements in CGM parameters (time in range and glucose variability) 142 without increasing hypoglycemia in T1DM subjects.

143 **1.2 Empagliflozin (SGLT-2 inhibitor) in TID**

144 Inhibitors of sodium-glucose cotransporter-2 have been approved for use in type 2 diabetes 145 where large clinical trials have demonstrated clinically significant improvements in glucose 146 control (viz., HbA1c) and cardiovascular events [7]. While not FDA approved for use in adults with 147 Type 1 diabetes subjects, these drugs have also been tested in randomized controlled clinical 148 trials in these patients to evaluate their safety and efficacy. The EASE program [8] included two

double-blind, placebo-controlled phase 3 trials in > 1700 patients with T1DM. These trials tested
2.5 mg, 10 mg and 25 mg tablets vs. placebo over 26-52 weeks. The results showed that
Empagliflozin lowered HbA1c, lowered total daily dose of insulin (by 10-13%) while increasing
time in range (by up to 12%) without any increase in the frequency or severity of hypoglycemia.
Simultaneously, there were improvements in body weight (by up to 3.5 Kg), blood pressure and
glucose variability.

155 However, adverse effects pertaining to genital infections, diabetic ketoacidosis, and ketosis 156 without acidosis were between 2-3 fold higher with Empagliflozin than placebo. Due to the 157 glycosuric effects of this class of drugs, it is noteworthy that the characteristic hyperglycemic milieu often seen during classical episodes of diabetic keto-acidosis are not observed in 158 ketoacidosis related to SGLT2 drug use where the ambient glucose concentrations are frequently 159 < 250 mg/dl. This observation has prompted the creation of the condition of "euglycemic diabetic 160 keto-acidosis" associated with SGLT2 drug use. Risks for development of ketosis were deemed to 161 be due to concomitant illnesses (viral infections, gastro-enteritis), insulin pump failure, alcohol 162 excess, extreme/endurance sports and low carbohydrate diet (< 100 grams/day). Suggestions for 163 164 prevention of ketosis in patients on SGLT2 inhibitor therapy are to avoid use of this class of drugs 165 in those with HbA1c > 9%, temporary drug discontinuation for 24-48 prior to planned surgery, fasting, intercurrent illnesses or prolonged physical activity, early recognition of symptoms of 166 167 ketosis (malaise, nausea, vomiting, abdominal pain, excess thirst), regular point of care ketone 168 monitoring (6-12 hourly) especially if glucose > 9mmol. The putative STICH protocol has recently 169 been recommended for management of diabetic ketoacidosis associated with use of SGLT2 170 inhibitor therapy [9]. This includes **ST**op drug, Inject bolus insulin (1.5 times the usual correction 171 bolus), **C**onsume 30-60 grams of carbohydrate and **H**ydrate with 200-500 ml of fluids. The above 172 sequence needs to be repeated every 1-2 hours with recheck of ketones in 2-4 hours. Medical 173 attention should be sought if any of the steps cannot be followed, particularly if fluids cannot be 174 maintained or if ketonemia does not resolve within 4-6 hours.

The increased risk of ketosis and DKA in SGLT2 users with T1DM may not preclude use of this class of drugs for the management of T1DM given their clinical benefits in RCTs in T1DM patients (described above) and the cardiovascular benefits in T2DM patients. As always, careful patient selection, patient education and monitoring strategies need to be developed and tested to ensure patient safety.

180 **1.3 Artificial Pancreas with Empagliflozin (SGLT2-i) use in T1D**

Adjuvant use of antidiabetic medications in combination with automated insulin delivery systems
 have been tested in short term clinical trials in T1DM. The drugs tested include pramlintide and
 GLP-1 receptor agonists [6]. To the best of our knowledge, there are no published clinical trials
 on the safety and efficacy of combining SGLT2 inhibitors with closed loop control. In contrast to

185 the above trials, where both pramlintide and GLP-1 agonists need to be infused or injected, 186 Empagliflozin, an SGLT2 inhibitor, is taken as a once daily oral tablet making it simple, practical 187 and not burdensome for patient adherence. Additionally, given its proven benefits on glucose 188 control in several large RCTs involving >1700 patients with T1DM, it is necessary to test its efficacy 189 and safety, in combination with automated insulin delivery systems, in T1DM subjects as part of 190 a clinical trial that we propose. Additionally, albeit the increased prevalence of ketosis with 191 empagliflozin use in the published trials, given the accumulated clinical information and 192 experience, we will ensure that appropriate precautions including judicious selection of research 193 participants (HbA1c of 9% as cutoff for enrollment), educating subjects on avoiding 194 circumstances that could predispose to ketosis (intercurrent illnesses, alcohol excess, low carb diet etc) and careful monitoring, will prevent and further lower the risks of ketosis during the 195 196 proposed, short term clinical trial.

197 **1.4 Basal-IQ with Empagliflozin use in T1D**

The Basal-IQ feature in the t:slim insulin pump reduce the frequency and duration of low-glucose events by predicting glucose levels 30 minutes ahead and suspending insulin if they are expected to drop below 80 mg/dL. Use of Empagliflozin during Basal-IQ phase is to explore its safety and feasibility as an adjunctive agent, compare its use vs Control-IQ phase and to gather data on its effect on postprandial glucose excursions.

203 **1.5 Study Objective**

[figure not shown]
The purpose of this study is to demonstrate the safety and efficacy of the use of Empagliflozin as
an adjunctive therapy with the Tandem t:slim X2 insulin pump with Control IQ Technology vs.
the Tandem t:slim X2 insulin pump with Basal-IQ Technology in T1D participants.

207 **1.6 Study Design**

The Main Study is a randomized control trial, aged 18 to 65 y.o. at time of consent, will be in the trial for up to 10 weeks. The first five participants will be enrolled in a Pilot Study to use the Basal-IQ with Empagliflozin 10 mg daily for approximately two weeks. These participants will participate in an estimated 36-48-hour hotel admission to initiate use of Closed Loop Control (CLC).

- The safety data from the Pilot Study will be presented to the DSMB for review. Upon DSMB approval, approximately 40 participants will be randomized 1:1 in a crossover design:
- 215 With Empagliflozin:
- 216 CiQ x 4 weeks (CiQ-EMPA) then Basal-IQ x 2 weeks (BiQ-EMPA)
- 217 Basal-IQ x 2 weeks (BiQ-EMPA) then CiQ x 4 weeks (CiQ-EMPA)

- 218 Without Empagliflozin:
- 219 CiQ x 4 weeks (CiQ-NO EMPA) then Basal-IQ x 2 weeks (BiQ-NO EMPA)
- 220 Basal-IQ x 2 weeks (BiQ-NO EMPA) then CiQ x 4 weeks (CiQ-NO EMPA)

221

222

Figure 1: Study Diagram

223 **1.7 Purpose/Objectives of Clinical Study**

224 **1.7.1 Study Participants**

- 225 Enrollment for the Pilot Study will proceed with the goal of completing approximately 5 226 participants in the trial.
- Enrollment in the Main Study will proceed with the goal of completing approximately 40 subjects,10 subjects in each group.
- 229 Up to 60 participants may sign the consent form.

230 **1.7.2 Clinical Sites**

231 The study will be performed at the University of Virginia.

232 **1.8 Primary Specific Aim**

233 CGM-measured time in the target range 70-180mg/dl (TIR) during the day

234 **1.9 Secondary Specific Aim**

- 235 24/7 CGM time in range <70mg/dl; 24/7 CGM-measured average glucose;
- 236 CGM-measured glucose variability (coefficient of variation, CV) during the day;
- 237 Risks for hypo- and hyperglycemia.

238 Chapter 2 Study Devices

239 2.1 Insulin Pump

The study system will include the Tandem t:slim X2 with Control-IQ Technology and Basal-IQTechnology.

242 **2.2 Continuous Glucose Monitor**

The study CGM will include Dexcom G6 transmitter and sensors while using the Tandem t:sliminsulin pumps. The CGM sensor is viable for 10 days.

245 **2.3 Blood Glucose Meter and Strips**

Blood glucose levels will be measured using the Bayer Contour Next blood glucose meter
(glucometer). The CGM device will be calibrated, if needed, using the study glucometer and strips
in accordance with the manufacturer's labeling.

249 **2.4 Ketone Meter and Strips**

Blood ketone levels will be measured using the Abbott Precision Xtra meters and strips in
accordance with the manufacturer's labeling. The blood glucose meter component of the
Precision Xtra Device will not be used.

253 **2.5 Study Devices Accountability Procedures**

254 Device serial numbers will be recorded and use of equipment will be tracked.

255 **2.6 Activity Tracker**

All subjects will be asked to wear a commercial activity tracker (e.g. Fitbit).

257 **Chapter 3 Study Medications**

258 **3.1 Insulin**

Participants will use either lispro or aspart insulin prescribed by their personal physician.Participants should bring their insulin to all study appointments.

261 **3.2 Empagliflozin – SGLT2-Inbitor**

262 Inhibitors of sodium-glucose cotransporter-2 have been approved for use in type 2 diabetes 263 where large clinical trials have demonstrated clinically significant improvements in glucose 264 control (viz., HbA1c) and cardiovascular events [7, 10]. These drugs have also been tested in 265 randomized controlled clinical trials in patients with Type 1 diabetes to evaluate their safety and 266 efficacy.

267 **3.3 Dosage**

Experimental group participants will be advised to take Empagliflozin (trade name: Jardiance) 5 268 269 mg one time daily, with or without food. Empagliflozin is available only in 10 mg and 25 mg film 270 coated unscored tablets. For this study, the participants will be provided 10 mg tablets and a pill 271 splitter. They will be instructed to split only 1 tablet at a time and take each half tablet (5mg each) 272 on subsequent days. Participants will be cautioned against spitting more than one tablet at a 273 time. Participants will be advised to take the medication only as prescribed. If a dose is missed, it 274 should be taken as soon as the participant remembers but will be advised not to double the next 275 dose.

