1026 Based on the facts that (1) adults and adolescents with diabetes experience mild hypoglycemia 1027 and hyperglycemia frequently as a consequence of the disease and its management, (2) the study 1028 intervention involves periodic automated insulin dosing that may increase the likelihood of 1029 hypoglycemia, and periodic automated attenuation of insulin delivery that may increase the 1030 likelihood of hyperglycemia, (3) mitigations are in place, and have been tested in prior studies 1031 using the investigational device system in the home setting, that limit the likelihood of excessive 1032 insulin dosing or prolonged withdrawal of insulin, and (4) rapid reversal of hypoglycemia and 1033 hyperglycemia can be achieved, it is the assessment of the investigators that this protocol falls 1034 under DHHS 46.405 which is a minor increase over minimal risk. In addition, it is the belief of the 1035 investigators that this study also presents prospect of direct benefit to the participants and general benefit to others with diabetes. 1036

1037 12.2 Potential Risks and Benefits of the Medication

1038 **12.2.1 Empagliflozin Adverse Reactions**

1039 The most recognized adverse reactions associated with the use of Empagliflozin are urinary tract 1040 infections and mycotic genital infections occurring in both men and women.

1041 Nausea, vomiting, abdominal pain, generalized malaise, acute febrile illness, reduced caloric 1042 intake due to illness or surgery, alcohol abuse, and shortness of breath may result in adverse 1043 reactions. The study physician may consider temporarily discontinuing Empagliflozin in any 1044 setting of reduced oral intake (such as acute illness or fasting) or fluid losses (such as 1045 gastrointestinal illness or excessive heat exposure).

After initiating therapy, participants will be monitored for increased urination and dehydration.
Participants will be informed that dehydration may increase the risk of hypotension and,
therefore, will be encouraged to increase their fluid intake while taking the medication.
Participates will also be advised that a majority of infections can be prevented by maintaining
attention to basic hygiene include regular washing after urination.

1051 Ketoacidosis is a common adverse reaction with the use of Empagliflozin. Ketone measurement1052 instructions are detailed in section 10.5.

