- 1115 Hypoglycemia and hyperglycemia not meeting the criteria below will not be recorded as adverse
- 1116 events unless associated with an Adverse Device Effect. Skin reactions from sensor placement
- 1117 are only reportable if severe and/or required treatment.

1118 **13.2.1 Hypoglycemia Event**

- Hypoglycemia not associated with an Adverse Device Effect is only reportable as an adverse eventwhen the following definition for severe hypoglycemia is met:
- 1121 The event required assistance of another person due to altered consciousness, and required
- another person to actively administer carbohydrate, glucagon, or other resuscitative actions;
- 1123 Impaired cognitively to the point that he/she was unable to treat himself/herself, was unable to
- 1124 verbalize his/ her needs, was incoherent, disoriented, and/or combative, or experienced
- seizure or coma. These episodes may be associated with sufficient neuroglycopenia toinduce seizure or coma;
- 1127 If plasma glucose measurements are not available during such an event, neurological recovery
- 1128 attributable to the restoration of plasma glucose to normal is considered sufficient evidence
- 1129 that the event was induced by a low plasma glucose concentration.

1130 **13.2.2 Hyperglycemia Events/Diabetes Ketoacidosis**

1131 Hyperglycemia not associated with an Adverse Device Effect is only reportable as an adverse 1132 event when one of the following four criteria is met:

- 1133 The event involved DKA, as defined by the Diabetes Control and Complications Trial (DCCT) and 1134 described below
- 1135 Evaluation or treatment was obtained at a health care provider facility for an acute event 1136 involving hyperglycemia or ketosis
- Blood ketone level ≥1.5 mmol/L and communication occurred with a health care provider at the
 time of the event
- Blood ketone level ≥3.0 mmol/L, even if there was no communication with a health care
 provider
- 1141 Hyperglycemic events are classified as DKA if the following are present:
- 1142 Symptoms such as polyuria, polydipsia, nausea, or vomiting
- 1143 Serum ketones ≥1.5 mmol/L or large/moderate urine ketones
- 1144 Ketosis as defined by symptoms and ketones regardless of treatment provided in a health care 1145 facility
- 1146 All reportable Adverse Events—whether volunteered by the participant, discovered by study
- 1147 personnel during questioning, or detected through physical examination, laboratory test, or

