- 1437 a. Studies have demonstrated reduced hepatic glycogen synthesis resulting in 1438 reduced net hepatic glycogen content in poorly controlled T1D compared to 1439 nondiabetic controls [16]. In contrast, in well controlled T1DM subjects, initial 1440 splanchnic glucose uptake was not reduced when compared to matched 1441 nondiabetic controls [17]. Taken together, assuming usual daily carbohydrate intake of ~ 180 grams (i.e., 60 grams per main meal) in an adult with T1DM, and a 1442 net splanchnic extraction of ingested carbohydrates of ~ 25% [17], ~ 75% of 1443 1444 ingested carbohydrates (~ 135 grams) would appear daily into the circulation. 1445 Given a relatively conservative estimate that ~ half the ingested carbohydrates are taken up by the peripheral tissues, that leaves ~ 70 grams of ingested 1446 carbohydrates/day to contribute to postprandial glucose excursions. 1447
- 1448b. Based on data obtained from the prescribing information of Empagliflozin that 101449mg of Empagliflozin results in net urinary loss of 64 grams of glucose per day [18],1450it is reasonable to assume that adjuvant use of this medication with Control-IQ or1451Basal-IQ would at least "double the effects" of lowering postprandial glucose1452concentrations in this clinical trial.

1453 Chapter 16 Data Collection and Monitoring

1454 **16.1 Case Report Forms and Device Data**

The study data are collected through a combination of case report forms (electronic and paper) and electronic device data files obtained from the software and individual hardware components. These electronic device files and electronic CRFs are considered the primary source documentation.

1459 When data are directly collected in electronic case report forms, this will be considered the 1460 source data. Records will be maintained in accordance with ICH E6 and institutional regulatory 1461 requirements for the protection of confidentiality of participants.

1462 **16.2 Study Records Retention**

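### Polyuria or polydipsia alone can meet the symptom part of the DKA definition, and both are made more likely by Empagliflozin or the advice given with it, so ketosis is more readily labelled DKA in Groups 1-2

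*Combined protocol and SAP*

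**What the plan says.** **The rule.** Section 13.2.2 opens its definition with "Hyperglycemic events are classified as DKA if the following are present". The first item is "Symptoms such as polyuria, polydipsia, nausea, or vomiting" and the second is "Serum ketones ≥1.5 mmol/L or large/moderate urine ketones". The third again rests on symptoms together with ketones, so it adds no independent test. As described there, the definition has no pH or bicarbonate criterion. Nothing asks that a symptom be new, worse than the participant's usual state on the drug, or unexplained by the drug.

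**The drug.** Section 12.2.1 says that after therapy starts "participants will be monitored for increased urination and dehydration". Because dehydration may bring hypotension, participants "therefore, will be encouraged to increase their fluid intake while taking the medication". Section 1.2 mentions the "glycosuric effects of this class of drugs, it is noteworthy that the characteristic hyperglycemic" picture, in a sentence that goes on to euglycemic ketoacidosis. The sample size rationale after section 15.6 states that 10 mg "of Empagliflozin results in net urinary loss of 64 grams of glucose per day"; the Main Study dose is 5 mg (section 3.3).

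**The controls.** Groups 3 and 4 take no Empagliflozin, and no placebo is described (sections 5.2 and 15.1).

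**Where DKA is used.** It is the first safety outcome in section 15.3.2 and is tabulated by treatment group in section 15.4. It also enters participant discontinuation (section 13.9.1) and the DSMB's review of individual events (sections 8.3 and 13.10).

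**The concern.** Above the ketone cut-off, the symptom part is what separates DKA from ketosis. A participant on the drug may pass more urine because of the drug and drink more because of the advice. If ketones then reach 1.5 mmol/L with no other complaint, the wording allows the event to be called DKA. A control with the same ketone value and no complaint has ketosis only. The definition is the same in both arms, but one of its criteria is affected by treatment, which is differential misclassification.

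The safety of the combination is part of the trial's primary purpose (section 15.1). Section 1.2 treats DKA and ketosis without acidosis as separate outcomes, and this rule blurs that line more in one arm than in the other. With 20 participants per arm, one event is 1/20 = 5 percentage points, so the labelling of one or two events could decide how the safety table reads.

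**Working it through.** The plan gives no figure to reproduce here. The check sets the passages side by side and then illustrates the effect under stated assumptions.

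**1. Can polyuria or polydipsia suffice?** Yes. The symptoms in 13.2.2 are examples joined by *or*, so one is enough once the ketone criterion is met.

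**2. Does treatment affect these symptoms?** For polyuria, plainly: section 12.2.1 plans monitoring for it on the drug. For polydipsia, less directly: the advice raises drinking, and section 10.5 also trains only experimental participants in the STICH steps, which include taking fluids. The form has no stated way to tell advised drinking from thirst.

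**3. How does this compare with the plan's own list?** For this drug class section 1.2 gives as symptoms of "ketosis (malaise, nausea, vomiting, abdominal pain, excess thirst), regular point of care ketone" monitoring. Polyuria is absent from that list; excess thirst is on it. The case is therefore stronger for polyuria than for polydipsia.

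**4. Illustration.** The documents give no rate, by arm, of either symptom or of ketones at 1.5 mmol/L or above. Assume an equal ketone risk *k* in both arms, at most one episode per participant, and a probability *s* that the symptom part is met in such an episode.

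- Classified DKA risk = *k* × *s*
- Chance of at least one among 20 = 1 − (1 − *ks*)^20; for *ks* = 0.03 this is 1 − 0.97^20 = 0.456

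With *k* = 10%:

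| *s*, control | *s*, drug | DKA risk, control | DKA risk, drug | Ratio | At least one of 20, control / drug |
|---|---|---|---|---|---|
| 30% | 50% | 3.0% | 5.0% | 1.67 | 46% / 64% |
| 30% | 70% | 3.0% | 7.0% | 2.33 | 46% / 77% |
| 30% | 100% | 3.0% | 10.0% | 3.33 | 46% / 88% |
| 50% | 70% | 5.0% | 7.0% | 1.40 | 64% / 77% |
| 50% | 90% | 5.0% | 9.0% | 1.80 | 64% / 85% |

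In the first three rows the expected number of cases is 20 × 0.03 = 0.6 on control, against 20 × 0.05 = 1.0 to 20 × 0.10 = 2.0 on drug. The excess of 0.4 to 1.4 cases arises from labelling alone. The ratio depends only on the two values of *s*. With *s* = 30% on control and 50-100% on drug, *k* = 5% gives 1.5% against 2.5-5.0%, and *k* = 20% gives 6.0% against 10.0-20.0%.

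**5. What else acts on the DKA count?**

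- *Towards fewer drug-arm cases:* the rule is worded for hyperglycemic events, while section 1.2 says ketoacidosis on this class frequently occurs below 250 mg/dl. Read literally, the wording could miss such cases.
- *Towards more drug-arm cases:* section 10.5 has drug participants test ketones at least twice and preferably four times daily, and controls each morning.

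The symptom effect is one of at least three, and the documents do not allow them to be summed.

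**The case against.** The strongest reply is that the bias has no established direction. Within hyperglycemic events controls can also have polyuria and thirst, which narrows the gap, and the hyperglycemia wording may lose drug-arm cases. This stands. A reader might infer that the rule overstates the drug's DKA excess, or that mislabelling can occur only on drug. The documents support neither; they support a symptom part met preferentially on drug.

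A reader might also infer that the symptom rule could trip the DSMB's 5% DKA limit. It cannot as written: section 8.3 defines DKA there by B-OH-B above 3 mmol, with no symptom element. Only the DSMB's review of individual events could be touched, and there the board can examine the case. Discontinuation after a single episode also requires a judgement that the drug caused it.

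Third, existing procedures help. Section 15.4 already summarises the circumstances of each DKA case, and a study physician checks every adverse event form. Symptomless ketosis is not wholly lost either: section 13.2.2 makes ketones of 1.5 mmol/L or above reportable if a provider was contacted, and 3.0 mmol/L or above in any case. This reduces the problem but does not remove it. A general summary of circumstances does not ensure that each symptom is recorded, and a physician who discounts drug-related urination does so by a judgement the plan does not describe.

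Finally, dropping events with only polyuria or polydipsia could discard genuine DKA, since excess thirst is on the plan's own list for ketosis. That also stands, and is why the reduced count should not replace the main one. No hypothesis test of DKA is planned in section 15.1, so this concerns a descriptive table.

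**Conclusion.** The point holds for the symptom part of the definition. At the same ketone value, that part is more easily met on Empagliflozin, and the 15.4 tabulation by arm inherits the difference. This follows from sections 13.2.2 and 12.2.1 and needs no assumed rates.

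The size is unknown. The ratios of 1.4 to 3.3 above rest wholly on assumed symptom probabilities, an equal ketone risk in both arms and one episode per participant. Section 1.2 reports DKA and ketosis two to three times as frequent on the drug as on placebo. It is tempting to infer that the artefact is as large as the real effect, but the overlap reflects the chosen inputs and is not evidence. Nor does the 64 g figure size the effect, because it refers to 10 mg and to glucose rather than symptoms.

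The net bias in DKA counts is not established. The change is still worth making, because it costs little and a symptom not recorded at the time may not be recoverable later.

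**What to change.** - **Form.** On the existing adverse event form, record each qualifying symptom separately, in both arms, before Main Study events are collected.
- **Section 15.4, main count.** Keep DKA as classified by 13.2.2 as the main tabulation by arm.
- **Section 15.4, sensitivity count.** Pre-specify a second count by arm that excludes events whose only qualifying symptom is polyuria and/or polydipsia. Report it beside the main count, not in its place.
- **Section 15.4, ketone count.** Add all events with ketones of 1.5 mmol/L or above, by arm, regardless of symptoms. The adverse event form alone will not supply this, since some such events are not reportable. Use the online ketone log and meter downloads of section 9.5, and state the unequal testing schedules beside the count.
- **Definitions.** Sections 8.3 and 13.2.2 define DKA differently. The sponsor and DSMB should reconcile them and state which applies where.

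The treatment, discontinuation and DSMB notification rules are left unchanged. The cost is one checklist and a few table rows. The drawback is that the sensitivity count may drop some genuine DKA, and it should be labelled accordingly.
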